6.1 Apremilast table of events**Schedule of Events**

Procedure	Screening phase	Baseline (Week 0)	Week 2	Week 4	Week 8	Week 12	Week 16	Week 24
Informed Consent	X							
Demography	X							
Medical History	X	X						
Inclusion/Exclusion Criteria	X	X						
Safety Assessments								
Adverse Events	X	X	X	X	X	X	X	
Vital Signs	X	X	X	X	X	X	X	X
Complete Physical Examination	X						X	X
Limited Physical Examination	X	X			X			
Weight	X	X	X	X	X	X	X	X
Hematology	X				X*		X*	
Serum Chemistry	X				X*		X*	
Urinalysis	X							
Pregnancy test	X						X*	
Contraception Education	X	X	X	X	X	X	X	
Efficacy Assessments								
Number of Oral Ulcers	X	X	X	X	X	X	X	X
Pain VAS for oral ulcers	X	X	X	X	X	X	X	X
Physician's Global Assessment of Oral Lesions	X	X	X	X	X	X	X	X
Chronic Oral Mucosal Disease Questionnaire – COMDQ	X	X			X		X	X
Investigational Product								
Dispense IP		X		X	X	X		
IP Accountability	X		X	X	X	X	X	

* lab work, including pregnancy testing, is optional per Investigator's discretion.

Statistical Plan

6.2 Sample Size Determination

A total of 15 patients will be enrolled in this study. This sample size will be sufficient in order to gain valuable data that could be used in the design of a future, larger study. Given the pilot/feasibility nature of the study, no formal power calculations were performed.

6.3 Statistical Methods

Data Analysis – Given the design, all statistical analysis will be descriptive. Continuous outcome measures will be summarized using the sample mean, standard deviation, median, minimum, 25th and 75th percentiles, and maximum. Categorical variables will be summarized with number and percentage. 95% confidence intervals (CIs) will be estimated where appropriate.

Descriptive Statistics

We will summarize continuous variables using the sample mean, standard deviation, median, minimum, 25th and 75th percentiles, and maximum. We will summarize categorical variables with number and percentages. Ordinal variables will be summarized using the sample median, minimum, 25th and 75th percentiles, and maximum, as well as with number and percentage.

Handling of Missing Data

Given the prospective nature of the study, we expect to encounter little if any missing data. However in the event of missing data, no attempt to impute this missing data will be made in this pilot study; missing data will be treated as missing.

Multiplicity

No adjustment for multiple testing will be made owing to the exploratory, pilot nature of the study.

Primary Hypothesis:

We hypothesize that apremilast administration for RAS will decrease the number of ulcers at the end of treatment compared to baseline.

The primary endpoints of the study is the change in number of ulcers at the end of treatment compared to baseline.

The secondary endpoints of the study, occurrence of adverse reactions and morbidity, are both dichotomous categorical variables. As such, the proportion for which these outcomes occur will be estimated along with 95% confidence interval.

Interim Analysis

No interim analysis will be performed in this pilot study.

6.4 Subject Population(s) for Analysis

All-treated population: Any subject randomized into the study that received study drug.

7 Safety and Adverse Events

7.1 Definitions

Unanticipated Problems Involving Risk to Subjects or Others (UPIRTSO)

Any unanticipated problem or adverse event that meets the following three criteria:

- Serious: Serious problems or events that results in significant harm, (which may be physical, psychological, financial, social, economic, or legal) or increased risk for the subject or others (including individuals who are not research subjects). These include: (1) death; (2) life threatening adverse experience; (3) hospitalization - inpatient, new, or prolonged; (4) disability/incapacity - persistent or significant; (5) birth defect/anomaly; (6) breach of confidentiality and (7) other problems, events, or new information (i.e. publications, DSMB reports, interim findings, product labeling change) that in the opinion of the local investigator may adversely affect the rights, safety, or welfare of the subjects or others, or substantially compromise the research data, **AND**
- Unanticipated: (i.e., unexpected) problems or events are those that are not already described as potential risks in the protocol, consent document, not listed in the Investigator's Brochure, or not part of an underlying disease. A problem or event is "unanticipated" when it was unforeseeable at the time of its occurrence. A problem or event is "unanticipated" when it occurs at an increased frequency or at an increased severity than expected, **AND**
- Related: A problem or event is "related" if it is possibly related to the research procedures.

Adverse Event

An untoward or undesirable experience associated with the use of a medical product (i.e. drug, device, biologic) in a patient or research subject.

Serious Adverse Event

Adverse events are classified as serious or non-serious. Serious problems/events can be well defined and include;

- death
- life threatening adverse experience
- hospitalization inpatient, new, or prolonged;
- disability/incapacity
- persistent or significant birth defect/anomaly

- important medical event

Important medical events are defined as those occurrences that may not be immediately life threatening or result in death, hospitalization, or disability, but may jeopardize the subject or require medical or surgical intervention to prevent one of the other outcomes listed above.

or other events that in the opinion of the sponsor-investigator may have adversely affected the rights, safety, or welfare of the subjects or others, or substantially compromised the research data.

All adverse events that do not meet any of the criteria for serious, should be regarded as **non-serious adverse events**.

Adverse Event Reporting Period

For this study, the study treatment follow-up period is 6 months after enrollment. The adverse event monitoring period will end at the end of the follow-up period. If an event is reported after this time it would need to be determined whether or not it is study related.

Preexisting Condition

A preexisting condition is one that is present at the start of the study. A preexisting condition should be recorded as an adverse event if the frequency, intensity, or the character of the condition worsens during the study period.

General Physical Examination Findings

At screening, any clinically significant abnormality should be recorded as a preexisting condition. At the end of the study, any new clinically significant findings/abnormalities that meet the definition of an adverse event must also be recorded and documented as an adverse event.

Post-study Adverse Event

All unresolved adverse events should be followed by the sponsor-investigator until the events are resolved, the subject is lost to follow-up, or the adverse event is otherwise explained. At the last scheduled visit, the sponsor-investigator should instruct each subject to report, to the sponsor-investigator, any subsequent event(s) that the subject, or the subject's personal physician, believes might reasonably be related to participation in this study.

Abnormal Laboratory Values

A clinical laboratory abnormality should be documented as an adverse event if it was exhibited as a severe reaction i.e. swelling, that required hospitalization or additional clinical intervention.

Hospitalization, Prolonged Hospitalization or Surgery

Any adverse event that results in hospitalization or prolonged hospitalization should be documented and reported as a serious adverse event unless specifically instructed otherwise in this protocol. Any condition responsible for surgery should be documented as an adverse event if the condition meets the criteria for an adverse event.

Neither the condition, hospitalization, prolonged hospitalization, nor surgery are reported as an adverse event in the following circumstances:

- Hospitalization or prolonged hospitalization for diagnostic or elective surgical procedures for a preexisting condition. Surgery should **not** be reported as an outcome of an adverse event if the purpose of the surgery was elective or diagnostic and the outcome was uneventful.

6/21/2017

- Hospitalization or prolonged hospitalization required to allow efficacy measurement for the study.
- Hospitalization or prolonged hospitalization for therapy of the target disease of the study, unless it is a worsening or increase in frequency of hospital admissions as judged by the clinical investigator.

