3.4 Primary Safety Endpoints

- Type, frequency, severity and relationship of the adverse events to apremilast
- Number of subjects who prematurely discontinue treatment due to any adverse event
- Frequency of clinically significant changes in vital signs and/or laboratory findings

4 Subject Selection Enrollment and Withdrawal

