7.2 Recording of Adverse Events

All adverse events will be documented as required, under 21 CFR part 1271. Depending on the nature and seriousness of the adverse reaction, the IRB will be notified according to the Mayo Clinic IRB policy. If An SAE occurs it will also be reported to the FDA as per regulations

At each contact with the subject, the study team must seek information on adverse events by specific questioning and, as appropriate, by examination. Information on all adverse events should be recorded immediately in the source document, and also in the appropriate adverse event section of the case report form (CRF) or separate worksheet. All clearly related signs, symptoms, and abnormal diagnostic, laboratory or procedure results should recorded in the source document.

All adverse events occurring during the study period must be recorded. The clinical course of each event should be followed until resolution, stabilization, or until it has been ultimately determined that the study treatment or participation is not the probable cause. Serious adverse events that are still ongoing at the end of the study period must be followed up, to determine the final outcome.

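### The laboratory criterion for an adverse event in Section 7.1 is narrower than the protocol's own adverse-event definition and could leave clinically significant laboratory changes out of the adverse-event counts

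*Combined protocol and SAP*

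**What the plan says.** Section 7.1 of the combined protocol and SAP has a paragraph headed Abnormal Laboratory Values. Its rule is that such a result "should be documented as an adverse event if it was exhibited as a severe reaction i.e. swelling, that required hospitalization or additional clinical intervention". No other section gives a criterion for when a laboratory result becomes an adverse event.

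The surrounding text uses other standards:

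- The general definition in Section 7.1 is "An untoward or undesirable experience associated with the use of a medical product", with no severity condition.
- For physical examination at the end of the study, Section 7.1 says that "any new clinically significant findings/abnormalities that meet the definition of an adverse event must also be recorded".
- Section 3.4 lists "Frequency of clinically significant changes in vital signs and/or laboratory findings" as a safety endpoint in its own right, beside "Type, frequency, severity and relationship of the adverse events to apremilast" and the number of subjects who stop treatment early because of any adverse event.
- Section 7.2 says "All adverse events occurring during the study period must be recorded". For clearly related findings it adds that "abnormal diagnostic, laboratory or procedure results should recorded in the source document".
- The schedule in Section 6.1 notes that "lab work, including pregnancy testing, is optional per Investigator's discretion". The note applies to hematology and serum chemistry at weeks 8 and 16, the only on-treatment visits at which they appear.

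**The concern.** A coordinator who holds a clinically significant but asymptomatic laboratory result gets two answers from Section 7.1. Under the general definition it can be an adverse event. Under the laboratory paragraph it does not meet the stated condition, because it was not a severe reaction. The specific rule is the one likely to be followed. Its wording is also hard to apply, because swelling is something seen on examination and not a value on a laboratory report.

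Four things depend on adverse-event status:

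- the first safety endpoint in Section 3.4 (adverse events by type, frequency, severity and relationship);
- the second (discontinuations due to adverse events);
- the proportion with adverse reactions, for which Section 6.3 plans a 95% confidence interval;
- the suspension rule in Section 7.4.

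Safety and tolerability is the secondary objective, and Section 6.2 says the data are meant to inform a larger study. A definition that leaves events out would carry into that design.

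**Working it through.** The plan gives no figure to reproduce, and Section 6.2 reports no power calculation. The check is therefore mainly a comparison of the text.

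**Step 1: thresholds side by side.**

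| Place | Applies to | Condition |
|---|---|---|
| 7.1, Adverse Event | any experience | untoward or undesirable, associated with the product |
| 7.1, General Physical Examination Findings | end-of-study findings | new, clinically significant, and meeting the adverse-event definition |
| 7.1, Abnormal Laboratory Values | laboratory abnormality | severe reaction, and hospitalization or further intervention |
| 3.4, third endpoint | vital signs and laboratory findings | clinically significant change |

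The laboratory rule has two cumulative conditions. Neither appears in the general definition or in Section 3.4. The examination rule refers back to the general definition and sets no severity or hospitalization condition of its own.

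**Step 2: where an excluded result goes.** Section 7.2 sends clearly related abnormal results to the source document. It names the adverse-event section of the case report form only for adverse events. A clinically significant change that fails the Section 7.1 rule should therefore still reach the third endpoint of Section 3.4. It would not reach the adverse-event totals, the discontinuations attributed to adverse events, or the trigger in Section 7.4.

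**Step 3: direction.** Following the narrower rule can remove events from those three places and cannot add any, so any error is an under-count.

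**Step 4: scale, for illustration only.** Section 6.2 gives n = 15, and I assume that all 15 are treated. Each subject whose only event is an excluded laboratory change lowers the adverse-event proportion by 1/15 = 6.7 percentage points. For discontinuations, suppose that one laboratory-driven stop goes uncounted. The exact (Clopper-Pearson) 95% limits are:

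- 1/15 = 6.7%. Lower limit: 1 − 0.975^(1/15) = 0.2%. Upper limit: the p that solves (1 − p)^15 + 15p(1 − p)^14 = 0.025, which is 31.9%.
- 0/15 = 0%. Lower limit: 0. Upper limit: 1 − 0.025^(1/15) = 21.8%.

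The documents give no expected number of such subjects, so the one subject is an assumption.

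**The case against.** The strongest reply is that the laboratory paragraph says *if* and not *only if*. Read literally, it gives one sufficient condition, while the general definition and the Section 7.2 duty to record all adverse events still apply. A reader might infer that the protocol expressly bars every other laboratory abnormality from being an adverse event. The text does not go that far. The restrictive reading is an inference, though the natural one: a stated threshold would serve little purpose if every clinically significant result counted anyway. On the broader reading, the two paragraphs of Section 7.1 still need reconciling.

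A reader might also infer that no laboratory value could ever meet the rule. The documents do not support that either. In its definition of unanticipated problems, Section 7.1 uses *i.e.* to introduce a list that reads as examples, so swelling may be only an example here. A severe abnormality that needed intervention without hospitalization could then qualify. The condition is narrow but not empty.

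Nor do clinically significant laboratory changes go unreported, because Section 3.4 counts them separately, and different thresholds for two endpoints are not in themselves a contradiction. This stands. But that count does not restore the adverse-event totals or the discontinuation figure. It is also a weak backstop: clinical significance is not defined, and on-treatment laboratory work is optional. Better wording cannot recover abnormalities that were never measured.

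Finally, the contrast between 1/15 and 0/15 is hypothetical, the two intervals overlap heavily, and Section 6.3 makes all analysis descriptive. That is right. The figures show scale and are not evidence that bias has occurred.

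**Conclusion.** The point holds as an inconsistency in safety recording. The only laboratory-specific criterion is narrower, on its natural reading, than the protocol's own adverse-event definition and than the laboratory standard in Section 3.4. If it is followed, clinically significant changes that were not severe reactions could be left out of the adverse-event counts and of discontinuations due to adverse events.

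The direction is an under-count. Its size cannot be derived, and one affected subject is worth 6.7 percentage points if all 15 are treated. The conclusion rests on sites applying the specific rule in preference to the general definition, and on such changes being detected when testing is optional. The loss is confined to results that depend on adverse-event status. It does not touch the primary efficacy endpoint, and the separate laboratory endpoint remains. The correction is worth making because a stated rule conflicts with the protocol's own definition and one sentence repairs it.

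**What to change.** In Section 7.1, Abnormal Laboratory Values, delete the reference to swelling and reword the sentence to agree with the general definition and Section 3.4. For example: a laboratory abnormality is documented as an adverse event when the investigator judges it clinically significant, or when it leads to intervention or to stopping study drug. This changes what is documented, not how subjects are managed.

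The direct cost is one sentence and a few more adverse-event entries. There is one further consequence. Section 7.4 suspends enrollment and treatment for a treatment-related adverse event and sets no severity threshold. A wider definition would let a related laboratory change trigger suspension. Sections 7.1 and 7.4 must therefore be reconciled together, and the sponsor-investigator should settle how they are meant to interact.

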7.2 Recording of Adverse Events

All adverse events will be documented as required, under 21 CFR part 1271. Depending on the nature and seriousness of the adverse reaction, the IRB will be notified according to the Mayo Clinic IRB policy. If An SAE occurs it will also be reported to the FDA as per regulations

At each contact with the subject, the study team must seek information on adverse events by specific questioning and, as appropriate, by examination. Information on all adverse events should be recorded immediately in the source document, and also in the appropriate adverse event section of the case report form (CRF) or separate worksheet. All clearly related signs, symptoms, and abnormal diagnostic, laboratory or procedure results should recorded in the source document.

All adverse events occurring during the study period must be recorded. The clinical course of each event should be followed until resolution, stabilization, or until it has been ultimately determined that the study treatment or participation is not the probable cause. Serious adverse events that are still ongoing at the end of the study period must be followed up, to determine the final outcome.

7.3 Reporting of Serious Adverse Events and Unanticipated Problems

When an adverse event has been identified, the study team will take appropriated action necessary to protect the study participant and then complete the Study Adverse Event Worksheet and/or log. The sponsor-investigator will evaluate the event and determine the necessary follow-up and reporting required.

The SAE must be reported immediately (i.e., within 24 hours of the Investigators' knowledge of the event) to Celgene Safety by facsimile. A written report (prepared by the Investigator(s) using an SAE Report Form or a 3500A Medwatch form is to be faxed to Safety (see below for contact information).

Celgene Drug Safety Contact Information:

Celgene Corporation
Global Drug Safety and Risk Management

██████████.
[name]

Fax: ██████████

E-mail: ██████████

7.3.1 Pregnancies

Pregnancies and suspected pregnancies (including a positive pregnancy test regardless of age or disease state) of a female subject or the female partner of a male subject occurring while the subject is on study drug, or within 30 days of the subject's last dose of study drug, are considered immediately reportable events. Study drug is to be discontinued immediately and the subject instructed to return any unused portion of the study drug to the investigator(s). The pregnancy, suspected pregnancy, or positive pregnancy test must be reported to Celgene Safety immediately facsimile using the Pregnancy Report form provided by Celgene.

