3.1 General Design

The study will be a pilot study using apremilast 30mg orally twice daily, for treatment of RAS in males and females between 18 and 70 years old.

Subjects will be recruited from the clinical practice of the Department of Dermatology or Division of Rheumatology at Mayo Clinic Florida. Fifteen males and females with RAS will be enrolled.

The study will consist of 3 phases: a screening phase, a 16 week treatment phase and an 8 week posttreatment observational follow-up phase.

The screening phase will consist of: obtaining informed consent, demographic information, medical history, inclusion and exclusion criteria, prior and concomitant medication use, adverse events; collecting vital signs and weight; performing complete physical examination and limited physical examination; obtaining hematology, serum chemistry, urinalysis, pregnancy test and providing contraception education.

During the 16-week treatment phase, all subjects receive apremilast.

All subjects who complete the active treatment phase are to enter the 8-week posttreatment observational follow-up phase.

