3.1.1 Contraception Education

The risks to a fetus or to a nursing child from apremilast are not known at this time. Results of the animal and in vitro studies can be found in the IB.

All females of childbearing potential (FCBP) must use one of the approved contraceptive options as described in section 4.1.1 while on investigational product (IP) and for at least 28 days after administration of the last dose of the IP.

When a female subject of childbearing potential's contraceptive measures or ability to become pregnant changes at the time of study entry or at any time during the study, the Investigator will educate the subject regarding options and correct and consistent use of effective contraceptive methods in order to successfully prevent pregnancy.

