4.1.1 Contraception Requirements

Females of childbearing potential^a (FCBP) must have a negative pregnancy test at screening. While on investigational product and for at least 28 days after taking the last dose of investigational product, FCBP who engage in activity in which conception is possible must use one of the approved contraceptive options described below:

Option 1 - Any one of the following highly effective methods: hormonal contraception (oral, injection, implant, transdermal patch, vaginal ring); intrauterine device (IUD); tubal ligation; or partner's vasectomy;

OR

Option 2 - Male or female condom (latex condom or nonlatex condom NOT made out of natural [animal] membrane [for example, polyurethane]; PLUS one additional barrier method: (a) diaphragm with spermicide; (b) cervical cap with spermicide; or (c) contraceptive sponge with spermicide.

^a A female of childbearing potential is a sexually mature female who has not undergone a hysterectomy or bilateral oophorectomy or has not been postmenopausal for at least 24 consecutive months.

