- e. At week 8 all patients will undergo safety assessments (adverse events, vital signs, limited physical examination, weight, contraception education, and optional lab work per Investigator's discretion, including hematology and serum chemistry), efficacy assessments (number of oral ulcers, pain visual analog scale for oral ulcers, physician's global assessment of oral lesions and Chronic Oral Mucosal Disease Questionnaire – COMDQ) and investigational product accountability. The investigational product will be dispensed.
- f. At week 12 all patients will undergo safety assessments (adverse events, vital signs, weight, and contraception education) and efficacy assessments (number of oral ulcers, pain visual analog scale for oral ulcers and physician's global assessment of oral lesions) and investigational product accountability. The investigational product will be dispensed.
- g. At week 16 all patients will undergo safety assessments (adverse events, vital signs, weight, complete physical examination, contraception education and optional lab work per Investigator's discretion, including pregnancy testing, hematology and serum chemistry), efficacy assessments (number of oral ulcers, pain visual analog scale for oral ulcers, physician's global assessment of oral lesions and Chronic Oral Mucosal Disease Questionnaire – COMDQ) and investigational product accountability.
- h. At week 24 patients will undergo safety assessments (vital signs, weight, and complete physical examination) and efficacy assessments (number of oral ulcers, pain visual analog scale for oral ulcers, physician's global assessment for oral lesions and Chronic Oral Mucosal Disease Questionnaire - COMDK).

6/21/2017

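### Pregnancies up to 30 days after the last dose are reportable, but no visit falls in that window for completers, and the week 24 schedule lists no adverse event or pregnancy item

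*Combined protocol and SAP*

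**What the plan says.** Section 7.3.1 applies to pregnancies, suspected pregnancies and positive tests "of a female subject or the female partner of a male subject occurring while the subject is on study drug". It then extends past treatment: "or within 30 days of the subject's last dose of study drug, are considered immediately reportable events". Such events go at once to the drug company's safety group on a dedicated pregnancy form.

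Section 3.1 sets out, after screening, "a 16 week treatment phase and an 8 week posttreatment observational follow-up phase". Only one visit follows week 16. Section 6 item h describes it: "At week 24 patients will undergo safety assessments (vital signs, weight, and complete physical examination) and efficacy assessments". The table in Section 6.1 agrees. Its week 24 column is blank for adverse events, pregnancy test and contraception education. After screening, the only pregnancy test is at week 16, and it is optional.

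Two general safety provisions bear on week 24. Section 7.1 ends adverse event monitoring only when follow-up ends. Section 7.2 requires the team to ask specifically about adverse events whenever it is in contact with a subject.

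On the reason for collecting these reports, Section 3.1.1 states: "The risks to a fetus or to a nursing child from apremilast are not known at this time".

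**The concern.** The protocol creates a duty to report pregnancies after the last dose but schedules no matching procedure. A site that follows item h and the table would not ask about adverse events at week 24, although Sections 7.1 and 7.2 say it should. A site that follows Section 7.2 would ask about adverse events but is nowhere told to ask about pregnancy. Neither route reaches the partners of male subjects.

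The protocol itself describes the fetal risk as unknown, so a missed report loses safety information that the trial means to collect. Because the answer is not recorded subject by subject, a count of zero at the end could mean that no pregnancy occurred or that nobody asked.

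Section 7.3.1 also leaves open what *occurring* means. If it means detection, a conception late in the 30 days that is recognised only afterwards falls outside the rule. If it means conception, that pregnancy is inside.

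**Working it through.** The plan states no figure to reproduce. The check is calendar arithmetic plus a comparison of sections.

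**Inputs**
- Treatment: 16 weeks (Section 3.1)
- Reporting window: 30 days after the last dose (Section 7.3.1)
- Final visit: week 24 (Section 6 item h; Section 6.1)

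**Timing for a subject who completes treatment**
- Last dose: 16 × 7 = day 112
- Window closes: 112 + 30 = day 142
- Week 24 visit: 24 × 7 = day 168
- Last dose to week 24: 168 − 112 = 56 days
- Window closing to week 24: 168 − 142 = 26 days
- Scheduled visits after day 112 and up to day 142: none

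**Sensitivity to treatment length.** Section 5.2 mentions 15 weeks at the full dose, so two other readings were tried:
- 5 days of titration plus 105 days: last dose day 110, window closes day 140, and week 24 is 168 − 140 = 28 days later.
- 105 days in total: last dose day 105, window closes day 135, and week 24 is 168 − 135 = 33 days later.

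Week 24 falls after the window on every reading. On these two, the week 16 visit (day 112) comes 2 or 7 days after the last dose, so it falls just inside the window but too early to cover the rest of it.

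**What each section provides at week 24**

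| Source | Adverse event inquiry | Pregnancy named | Partners of men |
|---|---|---|---|
| Section 6 item h | Not listed | No | No |
| Section 6.1, week 24 column | Blank | Blank | No |
| Section 7.1 | Monitoring still open | No | No |
| Section 7.2 | Required at each contact | No | No |
| Section 7.3.1 | – | Reporting duty only | Reporting duty only |

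The text of item h and the table agree with each other, so the blank cells are not an artefact of a broken table. The conflict is between those two and Sections 7.1 and 7.2.

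An optional test at the planned last dose in week 16 cannot detect a conception in the 30 days that follow.

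**The case against.** The strongest reply is that active inquiry does exist. Week 24 is a contact, so Section 7.2 requires adverse event questioning there. Section 7.1 keeps monitoring open and has subjects told at the last visit to report later events. A complete physical examination is scheduled at week 24, and contraception education is given at week 16, as the window opens. A reader might infer from the table that nothing after week 16 asks the subject anything. The documents do not support that, and Section 7.2 contradicts it.

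The reply does not close the gap. Section 7.1 does not define pregnancy as an adverse event, and Section 7.3.1 handles it separately. A partner's pregnancy is not an experience of the subject, so adverse event questions would not naturally reach it. The omission in item h and the table also remains at odds with Sections 7.1 and 7.2.

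A reader might also infer a contradiction between the 30-day reporting window and the contraception rule, which runs "for at least 28 days after taking the last dose of investigational product". There is none. Twenty-eight days is a minimum, the two rules serve different purposes, and both can be followed in full.

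It may also be tempting to define the window by date of conception alone. That could narrow the present rule: a pregnancy conceived after the screening test but before the first dose, and found on drug, is reportable now through the positive test and might cease to be.

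Three limits stand. Subjects who stop early but keep attending may have visits within their own 30 days. The absence of any partner inquiry applies to every visit, not only to week 24. The consent form, the pregnancy form and the separate safety-monitoring plan are not available here and may tell subjects to report promptly.

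**Conclusion.** The point holds as a gap in ascertainment and an internal inconsistency about week 24. For completers, no scheduled visit falls in the 30 days after the last dose, and the next one comes about 26 days after the window closes (26 to 33 days across the readings of treatment length). Until then, detection depends on the subject reporting. At week 24, the listed procedures omit adverse events, contrary to Sections 7.1 and 7.2, and no section has the team ask about pregnancy.

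The size is modest. The trial enrols 15 subjects, few pregnancies are expected, the documents give no rate from which to estimate a number, and no efficacy endpoint is affected. It is worth acting on because the information concerns an acknowledged unknown risk and the change costs almost nothing. The timing assumes that the last dose is taken at the end of the planned treatment period and that week 24 is attended on schedule.

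**What to change.** 1. Reconcile Section 6 item h and the week 24 column of Section 6.1 with Sections 7.1, 7.2 and 7.3.1 by listing adverse events at week 24.
2. Add one recorded question at that visit, put to women of childbearing potential and to male subjects about their partners: any pregnancy, suspected pregnancy or positive test since week 16, with dates.
3. State in Section 7.3.1 whether *occurring* refers to conception or detection, worded so that nothing now reportable is dropped. The choice is the sponsor's.

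The 28-day contraception wording needs no change on this account.

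The cost is one more question and one data field at a visit that already takes place, with no new visit or test. The change makes capture more complete and gives a recorded answer for each subject asked. It does not bring detection inside the 30 days.
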